7.1.3. Peripheral Oxygen Saturation (SpO₂) Sensor

Pulse oximetry is a non-invasive method of measuring the amount of hemoglobin saturated with oxygen or SpO₂. Light emitting diodes (LEDs) emit red and infrared light. Changes in light absorption during the pulsatile cyle determine the SpO₂.

The oxygen transducers (sensors) are available as a reusable or a disposable single use sensor.

Each study subject will be connected to the Capnostream monitor with a non-invasive SpO_2 disposable sensor applied to a finger (index finger preferred).

Figure 4. SpO₂ Sensor

Version 3.0, 29 Nov 2016

PRODIGY CIP

7.2. Intended Population

Intended Use

The Capnostream[™] 20p combined capnograph/pulse oximeter monitor and its accessories are intended to provide professionally trained health care providers with continuous, non-invasive measurement and monitoring of carbon dioxide concentration of the expired and inspired breath and respiration rate, and with continuous non-invasive monitoring of functional oxygen saturation of arterial hemoglobin (SpO₂) and pulse rate. It is intended for use with neonatal, pediatric, and adult patients in hospitals, hospital-type facilities, and intra-hospital transport environments.

The Capnostream[™] 35 is a portable capnograph/pulse oximeter, intended to provide professionally trained health care providers with continuous non-invasive monitoring of carbon dioxide concentration of the expired and inspired breath, respiration rate, arterial oxygen saturation (SpO2) and pulse rate of adult, pediatric , and neonatal patients. The pulse oximeter is intended for use during both no motion and motion conditions and for patients who are well or poorly perfused. The device is intended for use in hospitals, hospital-type facilities, during intra-hospital transport, and out-of-hospital Emergency Medical Service applications that include ground and air transport.

7.3. Equipment

Calibration information is provided in the Capnostream manual. Any additional maintenance or cleaning procedures should follow the operator's institution guidelines.

7.4. Product Use

Disposition or use of product provided to the site by the study sponsor is for study subject use only.

7.5. Product Training Requirements

Product information will be included in the study training materials. The device data transfer process will be tested and verified during the site initiation process. In addition, device data from the first ten subjects at each site will be collected and transferred through the device data transfer process as soon as

Version 3.0, 29 Nov 2016

PRODIGY CIP

COVMOPO0560

possible. This will be completed to ensure data quality and identify any process improvements to maximize quality, as needed.

7.6. Product Receipt and Tracking

Participating sites will be provided with a sufficient number of Capnostream monitors, if not already present. In addition, a sufficient number of etCO₂ sample lines and SpO₂ Sensors will be provided.

The following records will be maintained at minimum for product delivery, receipt and tracking at the site: dates, quantities received, lot/serial numbers, and expiration dates, as applicable.

7.7. Product Storage

Product provided to the site should be stored in a secured area with access limited to delegated study staff.

7.8. Product Return

Product provided to the site shall be returned at the end of the study. (Excludes consumable product that have been used during the course of the study). When returning the clinical study equipment the proper use of skids and pallets, as well as boxes or crates of the appropriate size and materials for their contents, will minimize damage to the equipment. Containers should be properly cushioned and braced for shock and vibration mitigation and adequately sealed and filled when possible with the weight evenly distributed.

Containers and inner pack material going out of the country should be used in conjunction with moistureresistant material such as desiccant and barrier bags. Straps, seals and shrink wrapping help minimize pilferage of the equipment during transport.

7.9. Product Accountability

Reconciliation of product received, used and returned will be completed at the end of the study.

8. Selection of Subjects

8.1. Study Population

The target population consists of subjects of adult age (\geq 18 in US and Europe, \geq 20 in Japan, \geq 21 in Singapore) receiving parenteral opioid therapy on the hospital ward for (post-surgical or non-surgical) pain.

8.2. Subject Enrollment

A subject is considered enrolled in the study once he/she signed the Informed Consent form and meets the inclusion/exclusion criteria.

PRODIGY CIP

The investigator may maintain a log of all subjects enrolled in the clinical investigation. A Subject Identification and Enrollment Log is a document to keep a confidential list of names of all subjects participating in the clinical study.

8.3. Inclusion Criteria

- 1. Patients receiving parenteral opioid therapy (for post-surgical or non-surgical) pain on the hospital ward.
- 2. Adult age (≥18 year old; ≥20 years old in Japan; ≥21 years old in Singapore).
- 3. Patient is able and willing to give informed consent.

8.4. Exclusion Criteria

- 1. Expected length of stay ≤ 24 hours.
- 2. Patient is receiving intrathecal opioids.
- 3. Post-surgical patients with American Society of Anesthesiologists physical status (ASA PS) V or higher.
- 4. Patients with the status of Do Not Resuscitate (DNR), hospice, or receiving end of life therapy.
- 5. Ventilated or intubated patients.
- 6. Patient is unwilling or unable to comply fully with study procedures (including non-toleration of the capnography cannula) due to any disease condition which can raise doubt about compliance and influencing the study outcome.
- Patient is a member of a vulnerable population, includinglegal incapacity or evidence that a subject cannot understand the purpose and risks of the study, regardless of authorized representative support.
- 8. Patient is participating in another potentially confounding drug or device clinical study.

9. Study Procedures

9.1. Schedule of Events

Data will be collected for Screening, Enrollment Visit, the Capnographic Monitoring Period, 1 month Follow Up Visit, and Study Exit. Additional data will be collected for Adverse Events, Device Deficiencies, and Protocol Deviations.

Data collection requirements are summarized in Table 2. The study site personnel must report all study specific Adverse Events and changes in status of these Adverse Events from time of enrollment until a subject exits the study.

Table 2. Data Collection Requirements

PRODIGY CIP

056-F275, Clinical Investigation Plan Template, Version 2.0

Data	Screening Evaluation	Enrollment	Capnography Monitoring	1 Month Follow up	Study Exit
Informed Consent	x				
Inclusion/Exclusion Criteria Evaluation	x				
Medical History		x			
Demographic & Physical Exam		x			
Vital Signs		x	x		
Supplemental Oxygen Use		x	x		
Surgery Information		x			
Care Pathway			x		
Monitoring Duration			x		
Medications		x	x		
Adverse Events		x	x	x	x
Device Memory Data			x		
Product Information			x		
Device Deficiencies			x		
Protocol Deviations	x	x	x	x	x
Healthcare Resource Utilization				x	x

9.2. Subject Screening

A consideration of all potential subjects is recommended to minimize selection bias. Track potential subjects on the Screening eCRF.

Version 3.0, 29 Nov 2016

If the patient is potentially eligible and willing to consider participation, written informed consent must be obtained. A review of subject files by the investigator is required to determine preliminary eligibility according to subject inclusion and exclusion criteria. Information included on the Screening Evaluation eCRF includes:

- Informed consent signature date
- Inclusion / exclusion criterial evaluation

Subjects will be considered a screen failure and immediately exited from the study if the subject signs the Informed Consent but fails to meet study inclusion/exclusion criteria prior to monitoring on the hospital ward. The reason for screen failure will be documented on the Screening Evaluation eCRF. Document the exit by completing the Study Exit eCRF.

9.3. Subject Consent

The investigator or authorized designee must obtain written informed consent before any clinical study related activity takes place. Written informed consent must be obtained prior to administration of opioid medication. In addition, written informed consent must be obtained pre-operatively, if surgery is applicable.

Well in advance of the consent discussion, the subject should receive the EC/IRB approved Patient Information and Informed Consent Form. During the consent discussion, the investigator or his/her authorized designee must fully inform the patient of all aspects of the clinical study that are relevant to the patient's decision to participate in the clinical study. If a patient is illiterate, an impartial witness must be present during the entire informed consent discussion. All items addressed in the Patient Information and the Informed Consent Form must be explained. The language used shall be as non-technical as possible and must be understandable to the patient and the impartial witness, where applicable.

The patient must have ample time and opportunity to read and understand the Patient Information and the Informed Consent Form, to inquire about details of the clinical study, and to decide whether or not to participate in the clinical study. All questions about the clinical study should be answered to the satisfaction of the patient.

Neither the investigator, nor the investigation site staff shall coerce or unduly influence a patient to participate or to continue to participate in the clinical study. The informed consent process shall not waive or appear to waive the patient's rights.

When the patient decides to participate in the clinical study, the Informed Consent Form must be signed and personally dated by the patient and investigator or authorized designee. If applicable, the witness shall also sign and personally date the consent form to attest that the information in the Patient Information and Informed Consent Form was accurately explained and clearly understood by the subject, and that informed consent was freely given.

After all persons have signed and dated the Informed Consent Form, the investigator must provide the subject with a copy of the Patient Information and the Informed Consent Form.

Medtronic will inform the investigators whenever information becomes available that may be relevant to the subject's confirmed participation in the clinical study. The investigator or his/her authorized designee should inform the subject in a timely manner.

PRODIGY CIP

Medtronic will revise the written Patient Information and Informed Consent Form whenever new information becomes available that may be relevant to the subject's confirmed participation in the clinical study. The revised information will be sent to the investigator for approval by the EC/IRB. After approval by the EC/IRB, a copy of this information must be provided to the participating subjects, and the informed consent process as described above needs to be repeated.

9.4. Prior and Concomitant Medications

Opioids, medications with sedative properties and concomitant pain medications will be documented on the Medication eCRF. In addition, administration of a reversal agent should be documented on the Medication eCRF.

Medications will be collected at study enrollment and during the monitoring period. In addition, for subjects who had surgery, medications relevant to the study used during surgery and recovery will be documented.

See appendice 2 for a list of potential medications.

9.5. Enrollment

The point of enrollment is informed consent completed and inclusion/exclusion criteria are confirmed per the screening evaluation.

Data collected for enrolled subjects includes:

- Medical history (including surgical, apnea, substance use, and medical therapy such as oxygen use and opioid use)
- Demographic & Physical exam
- Vital signs
- Supplemental oxygen use
- Surgery information (post-surgical subjects only)

9.6. Capnography Monitoring Period

Each subject will be clinically monitored through standard methods (as per clinical practice of the site). Additional continuous data from the Capnostream monitor will be collected for a maximum of 48 hours to identify potential indicators of respiratory depression.

Monitoring of capnography and pulse oximeter data with the Capnostream monitor will start after opioid therapy has been initiated for subjects that will receive their first opioid therapy dose while on the hospital ward. The monitoring period will start for subjects once they arrive on the ward, for those subjects where opioid therapy was initiated prior to arrival on the hospital ward.

Monitoring may be discontinued after a minimum of 4 hours from the last dose of opioid therapy received or if the subject is discharged from the hospital ward.

Monitoring duration may be determined in periods, as deemed clinically appropriate during opioid therapy. An example of monitoring split into three periods:

PRODIGY CIP

- Period 1: first 24 hours continuous monitoring after enrollment (mandatory).
- Period 2: 12 hours continuous monitoring (to be performed for guidance during the first night following Period 1, from 7pm to 7 am).
- Period 3: 12 hours continuous monitoring (to be performed for guidance during the second night following Period 1, from 7pm to 7 am).

The suggested monitoring setting for Periods 2 and 3 has been proposed to facilitate subject's motion during daytime, thus covering the nighttime period at higher risk of developing RD events⁶. The alarm feature of the monitoring device will be silenced and the screen information blinded. A periodic check during the monitoring period should be completed to ensure the etCO₂ filter line and SpO₂ sensor are appropriately fitted on the subject.

Apart from the capnographic monitoring, no other device or concomitant medications different from clinical practice may be used during PRODIGY Study.

The Monitoring eCRF will be completed to document:

- Care pathway (location/transfers within the hospital)
- Monitoring duration
- Vital signs
- Supplemental oxygen use
- Medications
- Product information

At the end of the monitoring period the subject will be treated according to the hospital clinical practice and remain in the study for a maximum period of 30 days from the start of opioid therapy.

9.7. 1-Month Follow Up

A 1 Month Follow Up visit (performed by phone if subject has been discharged) will be performed at 30 days (± 10 days) from enrollment.

Complete the 1 Month Follow Up eCRF. In addition, complete the applicable eCRFs to collect information related to:

- Adverse Events, if applicable to understand if any occurrence such as ORADE occurrence or mortality.
- Healthcare resource utilization (including hospital length of stay, readmission rate and related primary diagnosis).

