13.2. Data Analysis

A detailed description of the statistical methods will be contained in the Statistical Analysis Plan (SAP). Any change to the data analysis methods described in this section and/or the SAP will require an amendment only if it changes a principal feature of the study description. Any other changes to the data analysis methods will be described and justified in the Final Report or publication.

Based on the clinical practice in the opioid used and number of subjects enrolled per centre/country, an investigation of centre/country effect will be investigated including an independent variable for centres/country in the model as well as summary statistics if needed.

The choice of the imputation method for missing data will depend on the pattern of the missingdata and the type of the imputed variable.

The primary analysis will be performed on all subjects enrolled in the study and monitored with the Capnostream monitor and include all clinical outcomes that occur within the monitoring period(s) as for study design.

It is anticipated that SAS (SAS Institute Inc., Cary, NC, USA) will be used to perform all statistical analyses. Statistical tests will be based on a two-sided significance level of 0.05, and interaction effects will be evaluated at a significance level of 0.10. No adjustments for multiple comparisons will be performed. Additional exploratory analyses will be conducted as deemed appropriate.

The statistics above will be calculated by means of a GEE model as appropriate in order to take into account multiple events per subject and they will be reported together with the interval confidence (IC).

All assumptions for regression models will be assessed by viewing plots of the residual values.

Descriptive statistics will be used to summarize subject characteristics. This will include mean, standard deviation, median, minimum, and maximum for continuous variables, and counts and percentages for categorical variables. To compare subjects with and without the outcome, all categorical variables will be analyzed with the Chi-square test or the Fisher exact test or Cochran-Mantel-Haenszel test for trend for ordinal variables with 3 or more categories, as appropriate. Continuous variable parameter comparisons will be performed using t-test or Wilcoxon test according to the normal or non-normal distribution.

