7.1.3 Analysis Sets

The following subject sets will be used for the analysis:

- The Full Analysis Set (FAS) includes all patients enrolled in the study those sign Patient Informed Consent, fulfill the inclusion and exclusion criteria. The FAS will be used for safety evaluation.
- The Modified Full Analysis Set (MFAS) includes all patients enrolled in the study those sign Patient Informed Consent, fulfill the inclusion and exclusion criteria, start opioid therapy and monitored in the ward. Patients will not be excluded from the MFAS population even if prematurely stops, intermittent use or does not start the monitoring. Patients with major protocol deviations will be excluded from the MFAS. The MFAS will be used to evaluate the primary analysis.
- The Potential Respiratory Depression Population Set (PRDPS) includes all patients in the MFAS and have at least one Episode-File and/or Clinical Event to be adjudicated. The PRDPS will be used for secondary endpoint#2.

The following table shows how each population set will be used for analyses:

Population set	Baseline assessment	Primary and Secondary Endpoints (#1,#3)	Secondary Endpoint#2	Adverse Events
FAS	√			√
MFAS	√	√		√
PRDPS	√		√	

For those patients who have less than the minimum monitoring, or who drop out of the study, the analyses will include all data up to the point of their last data collection.

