7.6 Derived variables

The statistical evaluations will use some derived variables as listed below. All additional derived variables or changes on the variable listed below are reported in the Statistical Programming Requirements document.

New Variables	Derivation
Monitoring Exposure (minutes)	End monitoring date/time – Start monitoring date/time
Study Exposure (days)	(Study Exit date – date of enrollment)/30.44
BMI35	If BMI >35 then BMI35=1 otherwise BMI35=0
Obese	If BMI >30 then Obese=1 otherwise Obese=0
AGE50	If Age >50 then AGE50=1 otherwise AGE50=0
AGE65	If Age >65 then AGE65=1 otherwise AGE65=0
STOP BANG SCORE	The score is the sum of the following points for each patient: If Snoring loudly= Yes then add 1 point If Tiredness in daytime= Yes then add 1 point If Observed apnea during sleep= Yes then add 1 point If Treated for High blood Pressure= Yes then add 1 point If Body mass index >35 (kg/m2) then add 1 point If Age >50 years then add 1 point If Neck circumference >40 cm (16 inches/17inches according to gender) then add If Gender = Male then add 1 point
Opioids Tolerant §	The FDA definition will be used: A patient is considered opioid tolerant if for at least 1 week he/she has been receiving one of the following: 
 • 60 mg oral morphine/day • 25 mcg transdermal fentanyl/hour • 30 mg oral oxycodone/day • 60 mg oral hydrocodone/day • 8 mg oral hydromorphone/day • 25 mg oral oxymorphone/day • Equi-analgesic dose of any other opioid The Morphine Milligrams Equivalent will be used.
STOP BANG SCORE Class	If 0≤STOP-BANG score ≤2 then STOP BANG SCORE Class= 1 labeled as “Low risk of OSA” If 3≤STOP-BANG score ≤4 then STOP BANG SCORE Class= 2 labeled as “Intermediate risk of OSA” If 5≤STOP-BANG score ≤8 then STOP BANG SCORE Class= 3 labeled as “High risk of OSA”
High Risk Surgery	If occurred within 24 hours
Known or suspected sleep-disordered breathing§	if “Yes to OSA (from Medical History) + YES to first 4 questions of the Apnea History
PCA or epidural or intrathecal therapy	PCA with route as epidural or intrathecal from CM
Multiple opioid or concurrent CNS/sedating medication	According to the Medication coding *(benzodiazepines, sleep aids, muscle relaxant, etc.)
Opioid dosage	According to the Medication coding * (>30mg oral morphine per day or equivalent)
Major organ failure	According to the coding °
Diabetes	if “Yes to Diabetes type I or II”

New Variables§	Derivation

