7.10.1.1 Deriving the model

Note for Programmer: The analysis for the primary objective will be performed on a Dataset with one row per patient with RD episode as validated by CEC as the dependent variable (at least one RD) and baseline predictors as independent variables. Potential predictors will be reported on continuous scale or grouped into categories.

The logistic model will be used for bivariate e multivariate odds ratios (ORs) and 95% confidence intervals (95% CIs) will be estimated for each potential predictor. The following steps will be followed to derive the score for each predictor according to categories⁴:

- Determine categories for each risk factors (the most will be 0/1)
- Determine reference class for each risk factor (for dummy the reference category is 0)
- Calculate mid-values to represent categories
- Determine multiplier β
- Determine point score for each risk factor category

If **Data Split** approach:

- Repeat multivariate model on the validation set
- Calculate performance measures
- The "Optimism" is the difference between the performance measures from validation and derivation set

If **Bootstrapping** approach:

- 500 bootstrapped replications of the multivariate model

- Calculate performance measures bootstrapped
- The difference between the bootstrapped performance and the model performance will be averaged to obtain an estimation of the “optimism” of the model. The optimism will be used to validate the model.

Table 25 - RD Risk Score Derivation identified by logistic – MFAS

Predictors	Bivariate analysis OR (95% CI) (N=XXXX)	Multivariate analysis OR (95% CI) (N=XXXX)	Coefficient	Adjusted Coefficient	Risk score point
Char#1	x.xx (x.xx- x.xx)	x.xx (x.xx- x.xx)	x.xxx	x.xx (x.xx- x.xx)	xx
Char#2	x.xx (x.xx- x.xx)	x.xx (x.xx- x.xx)	x.xxx	x.xx (x.xx- x.xx)	xx
...					
Char#N	x.xx (x.xx- x.xx)	x.xx (x.xx- x.xx)	x.xxx	x.xx (x.xx- x.xx)	xx

The collinearity between categorical variables will be also tested by means the Cramer V test for nominal variables and Kendal’s tau-b for ordinal variables. The multivariate logistic regression model will be performed using a stepwise selection procedure in which the presence of event will be the dependent variable. Independent predictors will be entered in to the model if a significant association, defined as $p \leq 0.05$, will be identified from bivariate analysis and, to avoid over-fitted and unstable model the correlation coefficient between them should be less than 0.25.

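### Recorded monitoring time varies with the opioid course but is absent from the primary model, so predictors that go with longer recording can gain score points from observation time

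*Protocol*

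**What the plan says.** **Length of monitoring.** Under Protocol 9.6, Capnostream data "will be collected for a maximum of 48 hours". The same section states: "Monitoring may be discontinued after a minimum of 4 hours from the last dose of opioid therapy received or if the subject is discharged". It leaves the schedule to judgement: "Monitoring duration may be determined in periods, as deemed clinically appropriate during opioid therapy". It then gives an example in three parts. The first is "Period 1: first 24 hours continuous monitoring after enrollment (mandatory", and the other two are 12-hour nights with the days between left free for movement. The word mandatory appears only inside that example, and the 4-hour statement does not refer to it.

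**Primary model.** SAP 7.10.1.1 specifies a logistic regression and sets out its layout as follows: "one row per patient with RD episode as validated by CEC as the dependent variable (at least one RD) and baseline predictors as independent variables". Protocol 13.2 counts outcomes that fall within whatever monitoring took place.

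**Short or absent recordings.** SAP 7.1.3 keeps patients in the primary analysis set (MFAS) if they stop monitoring early, are monitored intermittently or do not start. On incomplete records it adds: "For those patients who have less than the minimum monitoring, or who drop out of the study, the analyses will include all data". The cut-off is each patient's final data collection. Protocol 13.2, by contrast, limits the primary analysis to enrolled subjects who were monitored with the device. SAP 7.4 does not impute the outcome.

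**Exposure.** SAP 7.6 derives Monitoring Exposure as "End monitoring date/time – Start monitoring date/time". SAP 7.8 puts it in a summary table and listing and describes signal gaps. It does not enter the primary model.

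**The concern.** The outcome is at least one RD over however long a patient was recorded. A patient recorded for 48 hours has more opportunity to show an RD than one recorded for 24, yet a negative result from either carries the same weight. A patient with no recording and no adjudicated clinical event would, on a literal reading, also enter as a negative.

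The imbalance need not be random. Recording may end a set time after the last opioid dose, and the candidate predictors in Protocol 13.1.1 include daily opioid dose, PCA or epidural or intrathecal therapy, and multiple opioids or sedatives. Patients with these features may well stay on opioids, and so on the monitor, for longer. SAP 7.6 also gives no time window for the medication-derived variables.

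At stake is the score itself, which is the primary objective. A predictor can pass the p ≤ 0.05 bivariate screen and collect points because it marks longer recording. A random 2:1 split, or 500 bootstrap samples, draws on the same patients with the same recording pattern. Internal validation would therefore repeat the bias and not reveal it.

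**Working it through.** **The plan's own figure.** 12 predictors × 10 events ÷ 0.12 = 1000 subjects for derivation, as Protocol 13.1.1 states. The 12% comes with no time window.

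**Inputs.** From the documents: 12% incidence, 48-hour maximum, 24-hour first period, points = round(10 × β), n = 1000, entry at p ≤ 0.05. Assumed: the 12% applies to 24 hours, the hazard is constant, half the patients carry the predictor, and the predictor has no effect on hourly hazard.

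**Chance of at least one RD.** P(24 h) = 0.12. P(48 h) = 1 − 0.88² = 0.2256.

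**Points gained by a predictor with no hourly effect:**

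- *All carriers recorded 48 h, all others 24 h.* OR = (0.2256/0.7744) ÷ (0.12/0.88) = 2.14. 10 × ln(2.14) = 7.6, so 8 points.
- *80% of carriers and 20% of others reach 48 h, the rest 24 h.* Risks are 0.8 × 0.2256 + 0.2 × 0.12 = 0.2045 and 0.2 × 0.2256 + 0.8 × 0.12 = 0.1411. OR = 1.56, 10 × ln OR = 4.5 (4.47 before rounding), so 4 points. The chance of p ≤ 0.05 is about 75%.
- *60% against 40%.* Risks are 0.1834 and 0.1622. OR = 1.16, 10 × ln OR = 1.5 (1.48), so 1 point. The chance of p ≤ 0.05 is about 15%.

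If the 12% is instead the overall incidence, full separation of 24 from 48 hours gives OR 2.09 and 7 points.

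**Front-loaded hazard.** Assume cumulative hazard proportional to 1 − exp(−t/16). At 24 h this is 0.777 and at 48 h 0.950, a ratio of 1.223. With 12% at 24 h, P(48 h) = 1 − 0.88^1.223 = 0.145. OR = (0.145/0.855) ÷ (0.12/0.88) = 1.24, about 2 points. With 12% as the overall incidence the result is again OR 1.24, with about a 19% chance of p ≤ 0.05.

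**Does an offset remove it?** In a simulation (600 runs, n = 1000, constant hazard, RD set to about 12% overall, monitoring SD 6 h, limited to 4–48 h), mean monitoring of 24 against 36 h gave a logistic β of 0.45, 4 points, and selection in 62% of runs. A complementary log-log model with offset log(total recorded hours) gave β 0.02, 0 points and 4% selection. With equal monitoring, both models selected the predictor in about 5% of runs.

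**Exposure variable.** On the example schedule with full nights, elapsed time is 24 h + gap to the next 19:00 + 12 h night + 12 h day + 12 h night = 60 h + gap. The gap runs from 0 to just under 24 h. So 48 recorded hours appear as about 60–84 h, an overstatement of 12/48 = 25% to 36/48 = 75%.

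**The case against.** The strongest reply concerns the target of estimation. Protocol 5.1.1 and SAP 4.1 aim to identify patients at risk of RD while on opioid therapy on the ward. That can be read as risk over the opioid course, not risk per recorded hour. A patient followed until at least 4 hours after the last dose has arguably been observed through the relevant period. If PCA or a high dose means a longer course and hence more RD, a tool for choosing whom to monitor may properly score that. In the first case above, the predictor with no hourly effect still separates a 23% risk from a 12% risk. This stands, and it is why the planned model need not be replaced. It does not cover recording that ended early for other reasons or never began.

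A reader might infer that short-course patients are watched for only a few hours, or that the score would mainly measure recording time. The documents do not support either. The 24-hour period is labelled mandatory, though within an example. Stays expected to last 24 hours or less are excluded, and the stopping statement is permissive. The dose predictor is a daily amount, and its link to the length of the course is plausible but not documented. The 8-point figure needs complete separation and a constant hazard, and Protocol 9.6 itself describes nights as higher risk.

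The exposure variable is descriptive only, and the Statistical Programming Requirements document, not available here, may refine it. That limits its effect on the primary result as planned, but end minus start would be unsuitable for any adjustment.

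**Conclusion.** The concern holds as a missing adjustment, not as proof of an invalid model. Recording time varies, is partly tied to the opioid course, and is ignored in the primary fit. The rate models in Protocol 13.4 serve secondary endpoints, and the GEE provision in Protocol 13.2 deals with repeated events.

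The size is conditional. Under a constant hazard with 12% RD in 24 hours, it runs from 1 point (60/40 mix) through 4 (80/20) to 8 (complete separation of 24 from 48 hours). Under the assumed front-loaded hazard, that last case falls to about 2. All of these respect a 24-hour floor, so enforcing one would not by itself remove the problem.

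It would go too far to conclude that the logistic model must give way to an hourly-hazard model. Part of any duration effect may be the risk the tool is meant to capture, and the documents cannot separate the two. An exposure-adjusted analysis beside the planned one would show how far the points depend on recording time.

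**What to change.** 1. **SAP 7.10.1.1.** Keep the planned fit as primary. Prespecify beside it a complementary log-log model with an offset of log(total recorded hours), and report which predictors lose or change points. State that the offset assumes a constant hazard. Use total recorded hours, not time to first RD: under SAP 7.10.1 and 9.4 the committee works in priority order and stops at the first confirmed RD, which need not be the earliest. An analysis limited to the first 24 hours is an optional further check. It avoids the constant-hazard assumption but may need extra adjudication.
2. **SAP 7.1.3 and 7.4.** Do not code patients with no recorded monitoring and no adjudicated event as free of RD. Treat their outcome as missing, or leave them out of model fitting in line with Protocol 13.2.
3. **SAP 7.6 and 7.8.** Define Monitoring Exposure as the sum of recorded intervals.
4. **Protocol 9.6.** Reconcile the 24 hours labelled mandatory with the 4-hour stopping statement.

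The cost is modest extra programming on device-memory data already collected, and a small loss of unrecorded patients from the model.
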